4.2 Follow-up procedures (by visits)

2 DAY & 1 MONTH FOLLOW UP CALL ADMINISTRATION PROTOCOL

Hello, _____. This is [NAME] calling from UNC Health Care. I'm calling about the Partners in Heart Health Research Study that you are participating in. Thanks again for participating in our study.

I'd like to ask you a few questions about your most recent appointment [interviewer to specify when the appointment was- e.g. 2 days ago]. Our conversation should take about 15 minutes. Is this a good time to talk?

Yes → [Continue]

No → [Reschedule interview for next available time- preferably within the same week]

During our conversation, I'll ask you questions about yourself, your visit companion, and your interactions with your provider. Your "visit companion" is the family member or friend that came with you to your appointment. Your provider is the doctor or nurse practitioner you saw during your visit.

2-Day Follow-Up Measures

1. Prompt List Acceptability
2. Satisfaction with visit
3. Perceptions of provider communication
4. Patient communication
5. Perceived efficacy in interactions with doctor
6. Self-efficacy related to self-care

The following protocol is for the administration of the 2 Day Follow Up and the 1 Month Follow Up Calls for each study participant.

Hello, _____. This is [NAME] calling from UNC Health Care. I'm calling about the Heart Failure Study that you joined earlier this year. My records show that your family member or friend had an appointment with their healthcare team 2-3 days ago. Is that right?

Yes → [Continue]

No → [Clarify appointment date and reschedule interview accordingly]

As part of the study, I'd like to ask you a few questions about your family member or friend's appointment. Our conversation should take about 15 minutes. Is this a good time to talk?

Yes → [Continue]

No → [Reschedule interview for next available time]

During our conversation, I'll ask you questions about yourself, your family member or friend who has heart failure, and your interactions with the doctor who treats your family member or friend's heart failure. We will use "doctor" to refer to the doctor, nurse practitioner, or physician assistant who your family member or friend usually sees during medical appointments.

[*Note that the 2-day follow-up questionnaires **for companions** includes the same measures, which parallel the patient questionnaires].

Prompt List Acceptability

1. **Do you remember receiving the "Preparing for Your Visit with Your Heart Doctor" checklist before your appointment?** **remember_list**
 Yes → **CONTINUE TO Q2**

- No → **READ BRIEF DESCRIPTION OF CHECKLIST (below), THEN ASK Q1 AGAIN. IF STILL “NO,” SKIP TO NEXT SECTION (SATISFACTION WITH VISIT).**

The “Preparing for Your Visit with Your Heart Doctor” checklist looks like a list of questions you can ask your doctor. Then, at the end, there is a section in which you can indicate what kind of help you would like from the person accompanying you to your appointment.

Relative Advantage					
2. Did the checklist make it easier or more difficult to talk to your doctor? Variable name: help_talk					
Much More Difficult					Much Easier
1	2	3	4	5	6
Compatibility					
3. The questions in the checklist matched the types of questions that you wanted to ask your doctor. good_questions					
Strongly Disagree					Strongly Agree
1	2	3	4	5	6
4. You had enough time to fill out the checklist in the waiting room before your appointment with your doctor. enough_time					
Strongly Disagree					Strongly Agree
1	2	3	4	5	6

--

Complexity

5. How much of the checklist did you fill out while waiting for your appointment with your doctor? *amount_done*

- All of it
- Most of it
- Some of it
- None of it → **SKIP TO Q8**

6. How easy or difficult was it to fill out the checklist? *ease_completion*

Very Difficult					Very Easy
1	2	3	4	5	6

7. The instructions on the checklist were clear and understandable. *clarity*

Strongly Disagree					Strongly Agree
1	2	3	4	5	6

8. How did you use the checklist during your visit with your doctor? *use_list*

- I handed the checklist to my doctor
- I asked my doctor questions by reading from the checklist
- I asked my doctor questions using my memory of the checklist
- I did not use the checklist when talking to my doctor → **SKIP TO Q13**

9. How easy or difficult was it to use the checklist when talking with your doctor? *ease_of_use*

Very Difficult					Very Easy
1	2	3	4	5	6

--

Trialability

10. You would use the checklist again at your next appointment with your doctor. *use_again*

Strongly Disagree					Strongly Agree
1	2	3	4	5	6

Observability

11. The checklist helped you to get more of your questions answered by your doctor. *get_answers*

Strongly Disagree					Strongly Agree
1	2	3	4	5	6

12. You were able to learn more during your appointment with your doctor because of the checklist. *learn_more*

Strongly Disagree					Strongly Agree
1	2	3	4	5	6

For these next questions, please think about the person who came with you to your appointment with your doctor.

13. How did you and your companion complete the checklist? *completion*

- We each filled it out separately
- We filled it out together
- We didn't fill it out at all → **Skip remainder of section**

14. Did you and your companion compare and discuss the checklist after filling it out? discuss_list
					

 Yes  No
					

15. After using the checklist, you have a better understanding of your companion's questions and concerns about your heart failure. understand_more
					
Strongly Disagree					Strongly Agree
1	2	3	4	5	6

16. You felt supported by your companion as a result of using the checklist. feel_support
					
Strongly Disagree					Strongly Agree
1	2	3	4	5	6

For participants who report in #13 that they did not complete the checklist:

1. What are some topics that you want to talk with your heart doctor about?

2. What topics are hardest to talk about? What topics are you most hesitant to talk about?

3. What some questions that you you like to ask your heart doctor?

Satisfaction with Visit

We are interested in your feelings, good and bad, about the medical care you have received. Think about the visit you had with your doctor a few days ago. How strongly do you agree or disagree with each of the following statements?

1. I was very satisfied with the medical care I received at my recent visit. *overall_satis*

Strongly disagree 1	Disagree 2	Uncertain 3	Agree 4	Strongly agree 5
------------------------	---------------	----------------	------------	---------------------

2. There were some things about the medical care I received at my recent visit that could have been better. *could_be_better*

Strongly disagree 1	Disagree 2	Uncertain 3	Agree 4	Strongly agree 5
------------------------	---------------	----------------	------------	---------------------

3. All things considered, the medical care I received at my recent visit was excellent *excellent_care*

Strongly disagree 1	Disagree 2	Uncertain 3	Agree 4	Strongly agree 5
------------------------	---------------	----------------	------------	---------------------

4. There were things about the medical system I received my care from that need to be improved *med_syst_improv*

Strongly disagree 1	Disagree 2	Uncertain 3	Agree 4	Strongly agree 5
------------------------	---------------	----------------	------------	---------------------

5. The medical care I received at my recent visit was just about perfect *perfect_care*

Strongly disagree 1	Disagree 2	Uncertain 3	Agree 4	Strongly agree 5
------------------------	---------------	----------------	------------	---------------------

6. I was dissatisfied with some things about the medical care I received at my recent visit
some_dissatis

Strongly disagree 1	Disagree 2	Uncertain 3	Agree 4	Strongly agree 5
------------------------	---------------	----------------	------------	---------------------

7. My doctor spent plenty of time with me during my recent visit. **satis_timespent**

Strongly disagree 1	Disagree 2	Uncertain 3	Agree 4	Strongly agree 5
------------------------	---------------	----------------	------------	---------------------

8. My doctor hurried too much during my recent visit **dr_hurried**

Strongly disagree 1	Disagree 2	Uncertain 3	Agree 4	Strongly agree 5
------------------------	---------------	----------------	------------	---------------------

Perceptions of Provider Communication

For these next questions, please think about the appointment you recently had with your heart doctor.

1. How much effort did your doctor make to help you understand your health issues?**dr_understand2**

No effort at all 0	1	2	3	4	5	6	7	8	Every effort was made 9
-----------------------	---	---	---	---	---	---	---	---	----------------------------

2. How much effort did your doctor make to answer your questions?**dr_answer2**

No effort at all									Every effort was made
0	1	2	3	4	5	6	7	8	9

3. How much did your doctor focus on the things that matter most to you about your health issues? **dr_focus2**

Not at all									Very much
0	1	2	3	4	5	6	7	8	9

4. How much did your doctor consider what matters most to you when choosing what to do next? **dr_consider2**

Not at all									Very much
0	1	2	3	4	5	6	7	8	9

Patient Communication

When answering the next set of questions, please continue to think about the visit you had with your doctor a few days ago. How strongly do you agree or disagree with each of the following statements?

1. I asked for recommendations about my medical condition **asked_recs2**

Strongly disagree									Strongly agree
0	1	2	3	4	5	6	7	8	9

2. I asked a lot of questions about my medical condition **asked_questions2**

Strongly disagree									Strongly agree
0	1	2	3	4	5	6	7	8	9

3. I went into great detail about my medical symptoms [detailed_sxs2](#)

Strongly disagree									Strongly agree
0	1	2	3	4	5	6	7	8	9

4. I asked the doctor to explain the treatment or procedure in greater detail [explain_tx2](#)

Strongly disagree									Strongly agree
0	1	2	3	4	5	6	7	8	9

5. I offered opinions to the doctor [offer_opinions2](#)

Strongly disagree									Strongly agree
0	1	2	3	4	5	6	7	8	9

6. I expressed concerns to the doctor [express_concern2](#)

Strongly disagree									Strongly agree
0	1	2	3	4	5	6	7	8	9

Perceived Efficacy in Interacting with Doctor

Next, I'd like to ask you some questions about your interactions with your doctor.

1. **How confident are you in your ability to know what questions to ask a doctor?** *know_to_ask2*

Not at all confident 0	1	2	3	Very confident 4
---------------------------	---	---	---	---------------------

2. **How confident are you in your ability to get a doctor to answer all of your questions?** *get_answers2*

Not at all confident 0	1	2	3	Very confident 4
---------------------------	---	---	---	---------------------

3. **How confident are you in your ability to make the most of your visit with a doctor?** *maximize_visit2*

Not at all confident 0	1	2	3	Very confident 4
---------------------------	---	---	---	---------------------

4. **How confident are you in your ability to get a doctor to take your health concerns seriously?** *take_serious2*

Not at all confident 0	1	2	3	Very confident 4
---------------------------	---	---	---	---------------------

5. **How confident are you in your ability to get a doctor to do something about your health concerns?** *make_dr_act2*

Not at all confident 0	1	2	3	Very confident 4
---------------------------	---	---	---	---------------------

6. **How confident are you in your ability to ask a doctor questions?** *able_to_ask2*

Not at all confident 0	1	2	3	Very confident 4
---------------------------	---	---	---	---------------------

1-MONTH FOLLOW-UP PATIENT QUESTIONNAIRE

1-Month Follow-up Measures

1. Self-care behaviors (Same measure as at baseline)
2. Self-efficacy related to self-care (Same measure as at baseline)
3. Communication with provider (Same measure as at baseline)
4. Emotional support
5. Tangible support
6. Perceived efficacy in interacting with doctor

Hello, _____. This is [NAME] calling from UNC Health Care. I'm calling about the Heart Failure Study that you joined earlier this year. This is the final part of the study, and I'd like to ask you a few questions about your health and your healthcare experiences. Our conversation should take about 15 minutes. Is this a good time to talk?

Yes → [Continue]

No → [Reschedule interview for next available time]

During our conversation, I'll ask you questions about yourself, your visit companion, and your interactions with your doctor. Your "visit companion" is the family member or friend who comes with you to your health appointments. Your "doctor" is the doctor, nurse practitioner, or other health care provider who you usually see during your visit.

4.3 **Unscheduled visits** N/A

4.4 **Concomitant Medication documentation** N/A

4.5 **Rescue medication administration (if applicable)** N/A

4.6 **Subject Completion/ Withdrawal procedures.** The total duration of study participation will be up to 6 months. Participants are eligible to withdraw at any time.

4.7 **Screen failure procedures.** For individuals who refuse or who are not eligible to participate, eligibility screening forms will be destroyed within 1 week of refusal or ineligibility is determined. We will keep a list of participant names who were approached and who are not eligible or not interested in participating so that they are not approached a second time.

5 **STUDY EVALUATIONS AND MEASUREMENTS (how measurements will be made)**

Data sources for this study include survey data and audio-taped data. Research staff will administer the surveys to study participants. We will use validated survey measures, where-ever possible. We will submit copies of all data collection instruments for IRB approval. We will not collect biometric or laboratory data as part of this study.

- 5.1 **Efficacy Evaluation (if applicable)** N/A
- 5.2 **Pharmacokinetic Evaluation (if applicable)** N/A
- 5.3 **Safety Evaluations** N/A

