key criteria for Inclusion and Exclusion:	
Receive care in the UNC Cardiology or General Internal Medicine practice
 
Have a clinical diagnosis of HF
 
Currently prescribe a loop diuretic
 
Have a New York Heart Association class II-IV
 
Must speak English
 
Must have a working telephone or live with the patient

	
Family Member Eligibility
 
Must be at least 18 years old and able to give informed consent
 
Must be willing to participate in the intervention activities and provide informed consent
 
Must speak English
 
Must have a working telephone or live with the patient

	
Health Care Provider Eligibility
 
Must be an MD or advance practice provider (NP or PA) in the UNC cardiology or General Internal Medicine practice
 
Must be willing to have an enrolled patient visit audio-taped

Number Of Subjects	Up to 80 participants, including up to 30 HF patients and family members, and HCPs
Study Duration	
Each subject’s participation will last up to 6 months
 
The entire study is expected to last 1 year

Study Phases Screening Study Treatment Follow-Up	
(1) Screening: screening for eligibility and obtaining consent and (2) Intervention: study intervention; and (3) 2-day post clinic visit and 1 month follow-up

Efficacy Evaluations	
Primary outcome: Percent of eligible patients and companions who enrolled in the study.
 
Secondary outcomes: 1) mean acceptability checklist score, 2) mean score on self-care of heart failure index scores (maintenance, management, and confidence subscales); 3) mean score on caregiver contribution to self-care of heart failure index scores (maintenance, management, and confidence subscales); 4) mean score on perceived efficacy in patient-physician interactions score; 5) mean score on communication with physicians measure

Pharmacokinetic Evaluations	N/A
Safety Evaluations	N/A
Statistical And Analytic Plan	This is a pilot study and as such, our sample size was selected based largely on feasibility. Specifically, we examined the expected margin of error for varying recruitment and recruitment yields.
DATA AND SAFETY MONITORING PLAN	We will not have a DSMC, DsMC, or DMC for this study given that the safety risk to participants is extremely low.

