4.1 Intervention/Treatment procedures (by visits)

PATIENT'S MEDICAL APPOINTMENT

The following protocol is for the administration of the study visit at the time of the patient's medical appointment.

Each dyad member will receive a prompt list to complete in the clinic waiting room immediately before their appointment. HF dyads will complete the prompt list without staff help. Completing the prompt list involves two steps. In step 1, participants will independently select from a list of questions or write in their own questions they would like to ask their health care provider during the visit. Patients will also be asked to select among a pre-determined list of behaviors they would like their family member to engage in during the visit (e.g., write down the providers instructions). In step 2, dyad members will collaboratively decide which questions to discuss during the visit. Participants will be encouraged to take the prompt list into the exam room and use it to facilitate communication with the HCP. The RA may take a picture of the prompt lists (which will not contain any identifying information, only a study id) to assess areas of agreement and disagreement between the dyad on what to discuss with the HCP.

The RA/SC will meet participants in the waiting room and introduce their self and review the directions of completing the prompt list with the participant(s) as well as the process of the data collection.

Note: If a participant has not completed an informed consent, one must be obtained prior to proceeding with the audio recorded medical appointment.

The RA/SC will obtain consent from the patient's HCP and remind the HCP that the appointment will be audio recorded. After the HCP has consented and the RA/SC has confirmed which exam room the patient will be in, the RA/SC can set up the audio recording equipment. When the HCP enters the room, the RA/SC will start the recording and exit the room. Once the appointment is over, the RA/SC will knock on the door and enter the exam room to stop the recording.

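### Willingness to use the checklist at the next visit (Q10) is asked only of people who used it with the doctor, so this part of the acceptability score describes users only

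*Combined protocol and SAP*

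**What the plan says.** Section 4.1 (Intervention/Treatment procedures) makes use of the list in the visit voluntary: "Participants will be encouraged to take the prompt list into the exam room and use it to facilitate communication with the HCP". Section 4.2 then collects acceptability by telephone about two days later.

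The form routes people at four places:

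- **Q1, recall.** Those who still do not recall the list after a description leave the section: "SKIP TO NEXT SECTION (SATISFACTION WITH VISIT").
- **Q5, amount filled in.** Those who filled in nothing pass over Q6 and Q7 but stay in the section: "None of it → SKIP TO Q8".
- **Q8, use with the doctor.** Those who did not use the list pass over Q9 to Q12: "I did not use the checklist when talking to my doctor → SKIP TO Q13".
- **Q13, joint completion.** Those who report that it was not filled in at all leave at this point: "Skip remainder of section".

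Q10 lies inside the block that Q8 removes: "You would use the checklist again at your next appointment with your doctor".

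The Synopsis lists "mean acceptability checklist score" as the first secondary outcome, and Section 6.2 repeats it. Section 6.3 plans percentages, means and standard deviations for acceptability. Neither section says how the score is built or how items skipped by routing count.

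**The concern.** Q9, Q11 and Q12 ask about the visit just held: how easy the list was to use, whether more questions were answered, whether more was learned. Not putting these to someone who did not use the list is acceptable. Q10 is different because it looks to the next appointment. A person who recalls the list, and perhaps filled it in, can say whether they would use it then.

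Acceptability is a stated objective. People who had the list in hand and did not use it are a group whose future willingness it would be useful to know. As the form stands, the answer comes only from people selected on having used the list, and no later analysis can supply the missing part.

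**Working it through.** **Step 1: trace the routing and count the rated items.** The items scored 1 to 6 are Q2, Q3, Q4, Q6, Q7, Q9, Q10, Q11, Q12, Q15 and Q16, which makes 11.

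| Path among people who recall the list | Rated items asked | Count |
|---|---|---|
| Filled in and used with the doctor | all | 11 |
| Filled in, not used | Q2-Q4, Q6, Q7, Q15, Q16 | 7 |
| Nothing filled in, not used | Q2-Q4 | 3 |

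**Step 2: look for another source of the Q10 answer.** Q13 and Q14 ask how the pair completed and compared the list. Q15 and Q16 concern the companion. The open questions that follow ask about topics to raise with the doctor. The listed 1-month measures contain no acceptability item. None asks about future use.

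**Step 3: effect on the mean acceptability score.** The plan gives no figure to reproduce. Every input here is an assumption:

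- non-use share f of 0.10 to 0.40 among people who recall the list;
- users average 5.0;
- non-users rate the other items 4.0 and would rate Q10 at 2.5;
- each person's score is the mean of the items they answered, and these scores are averaged over people.

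The overstatement equals f × [4.0 − (k × 4.0 + 2.5)/(k + 1)], where k is the number of items non-users answer now.

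- k = 7: (28 + 2.5)/8 = 3.8125, so the overstatement is 0.1875f. This is 0.019 at f = 0.10, 0.056 at 0.30 and 0.075 at 0.40.
- k = 3: (12 + 2.5)/4 = 3.625, so the overstatement is 0.375f. This is 0.038, 0.113 and 0.150.

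If non-users would instead rate Q10 at 4.5, above their other ratings, the sign reverses. At f = 0.40 the score is too low by 0.40 × 0.0625 = 0.025 (k = 7) or 0.40 × 0.125 = 0.050 (k = 3).

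**Step 4: the Q10 item taken alone.** With users at 5.0 and non-users anywhere from 1 to 6, the mean among all who recall the list lies between 5 − 4f and 5 + f, a width of 5f.

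| f | Range of Q10 mean | Width |
|---|---|---|
| 0.10 | 4.6 to 5.1 | 0.5 |
| 0.30 | 3.8 to 5.3 | 1.5 |
| 0.40 | 3.4 to 5.4 | 2.0 |

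If non-users would rate Q10 at 2.5, the users-only mean exceeds the mean for all who recall the list by f × 2.5, that is 0.25 to 1.00.

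**The case against.** The strongest defence is that the skip fits Q10 as worded. The item speaks of using the list again, its variable is use_again and it sits under Trialability, so it addresses people who tried the list in a visit. This has force for someone who filled in nothing. It has less for someone who completed the list in the waiting room, and the form itself treats such a person as having used it when it asks Q15: "After using the checklist, you have a better understanding of your" companion's concerns. Removing one word covers both groups.

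A reader might infer that recall at Q1 is the form's only gate, so that every later item was meant for everyone who recalls the list. The documents do not support this: Q8 is itself a gate on use, and Q2 to Q4 reach everyone because they come before it. The case rests on what Q10 asks.

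A reader might also take the wide ranges for Q10 as the error in the secondary outcome. They are not. The plan names the mean checklist score as the outcome and never the Q10 mean by itself. The shift in the score is small. With 30 patients and an assumed standard deviation of 1, its standard error would be 1/√30, about 0.18, which is larger than any shift in Step 3. No decision threshold is attached to acceptability.

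Finally, non-users are not invisible. Q8 counts them, and they rate three or seven other items. Labelling Q10 as a users-only result would prevent misreading, but it would not obtain the missing answers.

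**Conclusion.** The point holds as a minor one. The planned form collects its only item on future use from users alone, so Q10 and its contribution to the acceptability score cannot be read as the view of everyone who recalls the list.

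A reader might infer that acceptability is shown to be overstated. The documents do not establish that: upward bias requires non-users to be less willing, which is plausible but unproven, and the form does not record why a list went unused. The sizes in Step 3 rest wholly on assumed non-use, ratings and scoring rule. The missing scoring rule in Section 6.2 is a separate matter and adds no weight here.

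The companion form is not printed. Section 4.2 says that it parallels the patient form, so the same skip is presumed there rather than seen. Section 6.3 rules out hypothesis testing in this pilot.

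**What to change.** On the patient form, send Q8 non-users to Q10, worded for them without 'again', and then to Q13. Keep Q9, Q11 and Q12 for users. Make the same change on the companion form if it carries this skip.

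Report Q10 separately for users and non-users, with the number answering in each group. Label Q9, Q11 and Q12 as 'among users' and show the Q8 percentages beside them. For interviews already done, label Q10 'among users' as well.

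The cost is one skip target, one short reworded item, and submission of the revised form, since Section 5 sends data collection instruments for IRB approval. The non-user group will be small: 3 to 12 patients if 10% to 40% of 30 do not use the list. The acceptability figure may come out slightly lower.

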1.1 Name and Description of Investigational Product or Intervention

A question/topic prompt list is the main intervention in this study. A prompt list is a structured list of questions or topics related to illness, treatment, and support that the family member and/or patient may want to ask the HCP during the visit. The prompt list includes a section for the patient to check which behaviors they would like for their family member to engage in during the visit and space is provided for the family member to check which behaviors they are willing to perform during the visit.

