What support services are available in my community?	
Emotional Support	
How can I find a support group for people with heart failure?	
How can I find a support group for my caregiver, family members, or friends?	
What is the best way to tell my family and friends about my heart failure?	
Financial Support	
Who can help me with disability and unemployment benefits?	
How can I get help with insurance and medical bills?	
How can I get help affording my medications?	
Is there a way to reduce the cost of my current medications?	
Logistical Support	
Who can help me with transportation to and from medical appointments?	
Who can help me with transportation for other needs (such as running errands)?	
How can I find help with daily activities (such as cooking, running errands, etc.)?	
What types of adult daycare are available for me?	
Life Planning	
How can I help my family prepare if my heart failure gets really bad?	

Topic: Healthcare Team Roles and Responsibilities	Step 2: Select Your Questions
Who are the members of my healthcare team?	
What does each member of my healthcare team do? Who is responsible for what?	

Topic: Healthcare Team Roles and Responsibilities	Step 2: Select Your Questions
How can I find the right healthcare team if I'm moving to a new area?	
When should I...	
...call my heart doctor?	
...call my primary care doctor?	
...go to the hospital?	
...call 911?	

Step 3: Write Your Own Questions (Optional)	

Part 2: Help from Your Companion

Having a family member or friend accompany you to your medical appointment can be useful, especially if that person knows how to help. Below are some ways a companion might support you during your visit. Read through this list and put a checkmark next to the ways you'd like your companion to help.

✓	I would like my companion to...(check all that apply)
	Take notes on what the doctor says during my appointment.
	Remind me to ask my questions.
	Ask my doctor questions for me.
	Remind me to tell my doctor about my symptoms.
	Tell my doctor about my health.
	Make sure I understand what my doctor says.
	Stay in the waiting room for part of the visit.
	Other ways you would like your companion to help you: _____ _____ _____
	I don't need my companion to help me during my visit.

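### Acceptability item Q8 gives the patient no way to report using the list through the companion, so such patients skip four of the eleven six-point ratings

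*Combined protocol and SAP*

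**What the plan says.** Section 1.1 describes the intervention as a list of questions or topics plus a section on companion help. The patient ticks the help wanted, and "space is provided for the family member to check which behaviors they are willing to perform during the visit". The patient list reproduced in Section 4.1 (Intervention/Treatment procedures) names seven specific kinds of help in Part 2. Two of them are "Ask my doctor questions for me" and "Take notes on what the doctor says during my appointment".

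The 2-day questionnaire in Section 4.2 asks at Q8 how the list was used during the visit. The positive answers are "I handed the checklist to my doctor", "I asked my doctor questions by reading from the checklist" and "I asked my doctor questions using my memory of the checklist". The remaining answer, "I did not use the checklist when talking to my doctor", carries an instruction to skip to Q13. No answer covers use through the companion, there is no category for other use, and nothing says whether several answers may be given.

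For companions, Section 4.2 says only that the 2-day questionnaire "includes the same measures, which parallel the patient questionnaires"; the companion wording is not reproduced. Section 6.2 makes the mean acceptability score the first secondary outcome.

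**The concern.** The list is meant to be used by a pair. Each member fills in a list, the two decide together what to raise, and Part 2 lets the patient hand parts of the conversation to the companion. Q8 treats use as something the respondent does alone. A patient who delegates the asking, as Part 2 allows, can truthfully give only the last answer, and the skip then withholds the ratings of ease of use, use again, questions answered and learning.

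What is at stake is who supplies those four ratings. A patient who followed the list's own invitation drops out of them, while a patient who spoke personally stays in. In a pilot meant to judge acceptability for patients and families, that is a selective loss, and it falls on a way of using the list that the design encourages.

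**Working it through.** The plan gives no figure for this point, so there is nothing to reproduce. The check sets the items side by side and counts them.

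**Step 1: ratings on the form.** The items in Prompt List Acceptability answered on a 1 to 6 scale are Q2, Q3, Q4, Q6, Q7, Q9, Q10, Q11, Q12, Q15 and Q16, which makes 11.

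**Step 2: ratings removed by the skip.** Going from Q8 to Q13 omits Q9, Q10, Q11 and Q12, all of them six-point ratings. The loss is 4 of 11, or 4/11 = 36%, and 11 − 4 = 7 ratings remain available. Q15 and Q16 are still reached unless Q13 is answered that the list was not filled out at all.

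**Step 3: does the skip fit the omitted items?** Q9 asks about ease of use in the respondent's own conversation with the doctor, so skipping it can be defended for someone who did not speak from the list. Q10 (use again), Q11 (more questions answered) and Q12 (learned more) do not require that the respondent did the asking. A patient whose companion asked could answer all three.

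**Step 4: who is affected?** Only a patient who did none of the three first-person things. One who was reminded by the companion and then asked fits the second or third answer and is kept. So is one who asked from the list while the companion took notes.

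**Step 5: where companion-mediated use appears elsewhere.**

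| Source | What it can show | What it leaves out |
|---|---|---|
| Companion's parallel Q8 (wording inferred) | That the companion asked from the list | The patient's Q9 to Q12 |
| Q16 | Overall feeling of support from using the list | Which kind of help was given |
| Audio recording and the second paper (Section 12) | Questions asked against questions both members marked | Help other than asking, as the comparison is described |

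Of the seven kinds of help in Part 2, the companion's Q8 would directly capture one, the asking of questions. The other 7 − 1 = 6 (notes, two kinds of reminder, telling the doctor about the patient's health, checking understanding, staying in the waiting room) have no specific follow-up item.

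**Step 6: size.** If k patients used the list only through the companion, 4k patient ratings are lost. With 30 patients, Q9 to Q12 could yield at most 30 × 4 = 120 patient ratings, so each affected patient removes 4/120 = 3.3% of them. The documents give no value for k.

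**The case against.** The strongest reply is that much of this information exists elsewhere. A reader might infer that use through the companion is measured nowhere else. The documents do not support that. The companion has a parallel list and a parallel 2-day questionnaire, Q16 survives the skip, completed lists are copied, and the planned second paper compares questions asked with questions that patients and companions marked. Where the companion did the asking, the study has two routes to that fact.

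A reader might also infer that the study will understate a reported rate of use, or that half of the intervention goes without a planned result. Neither follows. No endpoint is a percentage of users, and no written rule classifies the last Q8 answer for any reported rate. Part 2 is one section after several pages of questions, and the share of requested help that was given is not an aim or endpoint of the plan. It is also not established that a note-taking companion is recorded as a non-user, because the companion's wording is not shown.

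Finally, the affected group may be small, since a patient who did any of the three listed things is kept.

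All of this stands and limits the point. It does not remove it: none of the other sources supplies the patient's own answers to Q9 to Q12, and the skip that withholds them is written into the form.

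**Conclusion.** The point holds in a limited form. The patient's Q8 has no answer for use through the companion although Part 2 invites such use. A patient who used the list only in that way is routed past 4 of 11 six-point ratings (36%), so on the patient form those four describe direct users only. Companion question-asking can be partly recovered from other sources and overall support from Q16. Note-taking, reminders and checking understanding have no specific follow-up item.

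This rests on the skip being applied as printed and on the patient having done none of the three first-person things. The number affected is unknown. The direction of any effect on the mean acceptability score is also unknown, because the plan does not say how the mean is formed when items are skipped. The primary outcome, enrollment, is untouched. This is a cheap improvement to an instrument and does not threaten the study's conclusions.

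**What to change.** On both the patient and companion forms:

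- State at Q8 that more than one answer may be given.
- Add an answer for questions from the list being asked by one member on behalf of the other, worded for the respondent (my companion asked for me; I asked for the patient).
- Add an answer for help of the kinds ticked in Part 2 being given, again worded for each respondent.
- Apply the skip to Q13 only when no kind of use is reported.

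Under the revised skip, Q9 may not fit a respondent who did not speak from the list, so a not-applicable answer there would be sensible.

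The cost is an instrument amendment and a slightly longer 2-day call, which is already scheduled. A tick-list asking which Part 2 behaviors took place would be a useful optional addition if the investigators want to describe how companion help worked. It goes beyond the outcomes the plan sets and is not needed to correct Q8.
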